7.0 Protocol Treatment

7.1 Treatment Schedule - Cycle length = 28 days

7.11 Phase I - Dose Escalation

Agent	Dose	Route	Days
Lenalidomide	25 mg	PO	Days 1-21
Dexamethasone	20 mg (SMM and IMM); 40 mg (Active MM)	PO	Days 1, 8, 15, and 22
Anakinra	As assigned by MCCC Registration Office	SQ	Days 1-28
Aspirin	325 mg/day with food	PO	Days 1-28

7.12 Phase II Study at MTD/MAD

Agent	Dose	Route	Days
Lenalidomide	25 mg	PO	Days 1-21
Dexamethasone	20 mg (SMM and IMM); 40 mg (Active MM)	PO	Days 1, 8, 15, and 22
Anakinra or Placebo	Based on phase I results	SQ	Days 1-28
Aspirin	325 mg/day with food	PO	Days 1-28

7.2 Determination of Maximum Tolerated Dose (MTD)/Maximum Allowable Dose (MAD)

7.21 Dose Escalation

Dose Level	Dose of anakinra
1*	100 mg SQ every 3 rd day
2	100 mg SQ every other day
3	100 mg SQ daily

*Starting dose

7.211 For this protocol, the patient must return to the consenting institution for evaluation at least every 28 days during treatment (Active Monitoring Phase).

7.212 Treatment by a local medical doctor (LMD) is not allowed.

7.213 Three patients will be treated at each dose level and observed for a minimum of 4 weeks (i.e. one full cycle), to assess toxicities, before new patients are treated. Doses will not be escalated in any individual patient.

7.214 Investigators are to contact the Study Chair as soon as any dose-limiting toxicity (DLT) occurs.

7.22 Definition of DLT – See Section 16.22 for additional information

For this protocol, DLT will be defined as an adverse event during Cycle 1 of treatment at least possibly related to the study medication and meeting the following criteria:

Toxicity*	DLT Definition
Blood and lymphatic system disorders	Grade 3 Febrile neutropenia: ANC <1000/mm ³ with a single temperature of >38.3 degrees C (101 degrees F) or a sustained temperature of ≥38 degrees C (100.4 degrees F) for more than one hour
Investigations	Grade 4 neutropenia (ANC <500/mm ³) for ≥7 days or Grade 4 thrombocytopenia (<25,000/mm ³) for ≥7 days
Infection and infestations	Grade 4
Other Non-hematologic	Grade 4 as per NCI Common Terminology Criteria for Adverse Events v 4.0**
Dose Delay	Any toxicity that causes a dose delay of >2 weeks of the next intended dose.***
Dose Reduction	Any dose reduction within cycle 1.***

*Adverse event at least possibly related to the study medication.

**Grade 4 vomiting or diarrhea with maximal supportive treatment(s) will be considered dose limiting.

***Except dose reductions and delays due to rash associated with lenalidomide. These patients will be replaced with another study patient.

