8.0 Dosage Modification Based on Adverse Events

Strictly follow the modifications in this table for the first **two** cycles, until individual treatment tolerance can be ascertained. Thereafter, these modifications should be regarded as guidelines to produce mild-to-moderate, but not debilitating, side effects. If multiple adverse events are seen, administer dose based on greatest reduction required for any single adverse event observed. Reductions or increases apply to treatment given in the preceding cycle and are based on adverse events observed since the prior dose.

ALERT: *ADR reporting may be required for some adverse events (See Section 10)*

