8.2 Dose Modifications of Lenalidomide during a Cycle of Therapy

Dose reductions of one drug and not the other may be done at the investigators discretion based on attribution of adverse events except neutropenia in which lenalidomide should be decreased first before anakinra.

→ → Use the NCI Common Terminology Criteria for Adverse Events (CTCAE) version 4.0* unless otherwise specified ← ←

CTCAE System/Organ/Class (SOC)	ADVERSE EVENT	AGENT	ACTION** Days 2-14 of cycle	ACTION** Day ≥15 of cycle
Blood and lymphatic system disorders	Febrile neutropenia associated with fever (temperature ≥38.5°C)	Lenalidomide	Omit lenalidomide dose. Follow CBC weekly. If neutropenia has resolved to ≤Grade 2 prior to Day 21, restart lenalidomide at next lower dose level and continue the cycle through Day 21. If neutropenia is the only toxicity for which a dose reduction is required, G-CSF may be used and the lenalidomide dose maintained	Omit lenalidomide for remainder of cycle. See Section 8.11 for Initiation of a New Cycle and reduce the dose of lenalidomide by 1 dose level. If neutropenia is the only toxicity for which a dose reduction is required, G-CSF may be used and the lenalidomide dose maintained for the next cycle at the investigator's discretion.
Investigations	Platelet count decreased ≥ Grade 3 (platelet count <50,000/mm ³)	Lenalidomide	Omit lenalidomide dose Follow CBC weekly Hold anticoagulation until platelets >50,000 If thrombocyte-penia resolves to ≤Grade 2 prior to Day 21, restart lenalidomide at next lower dose level and continue the cycle through Day 21	Omit lenalidomide for remainder of cycle See Section 8.11 , Instructions for Initiation of a New Cycle and reduce the dose of lenalidomide by 1 dose level

CTCAE System/Organ/Class (SOC)	ADVERSE EVENT	AGENT	ACTION** Days 2-14 of cycle	ACTION** Day \geq 15 of cycle
Skin and subcutaneous tissue disorders	Rash maculo papular Grade 2 or 3.	Lenalidomide	Omit lenalidomide dose Follow weekly If the event resolves to \leq Grade 1 prior to Day 21, restart lenalidomide at next lower dose level and continue the cycle through Day 21	Omit lenalidomide for remainder of cycle See Section 8.11 , Instructions for Initiation of a New Cycle and reduce the dose of lenalidomide by 1 dose level
	Any rash Grade 4	Lenalidomide	Discontinue lenalidomide	Discontinue lenalidomide

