8.4 Dose Modifications of Dexamethasone during a Cycle of Therapy

CTCAE System/organ/Class (SOC)	ADVERSE EVENT	AGENT	ACTION ** (each cycle)
Gastrointestinal Disorders	Dyspepsia, gastric or duodenal ulcer, gastritis Grade 1-2 (Symptomatic; altered GI function; medical intervention indicated; limiting instrumental ADL)	Dexamethasone	Treat with H2 blockers, sucralfate, or omeprazole If symptoms persist despite above measures, decrease dexamethasone dose by 50%
	Dyspepsia, gastric or duodenal ulcer, gastritis ≥Grade 3 (Severely altered GI function; TPN indicated; elective operative or endoscopic intervention indicated; limiting self-care ADL; disabling)		Omit dexamethasone until symptoms adequately controlled Restart one dose level below along with concurrent therapy with H2 blockers, sucralfate, or omeprazole If symptoms persist despite above measures, decrease dex by 50%
	Pancreatitis ≥Grade 3 (severe pain; vomiting; medical intervention indicated (e.g., analgesia, nutritional support))		Discontinue dex, and begin event monitoring
General Disorders	Edema ≥Grade 3 (limiting function and unresponsive to therapy or anasarca)		Decrease dex by 50%; use diuretics prn
Psychiatric Disorders	Confusion or Mood alteration ≥Grade 2 (Severe disorientation; limiting self-care ADL)		Omit until symptoms resolve; Decrease dex by 50%
Musculoskeletal and connective tissue disorders	Muscle weakness ≥Grade 2 Weakness limiting self-care ADL; disabling		Decrease dex by 50%; if symptoms persist then decrease 50% prn
Eye Disorders	Blurred vision ≥Grade 3		Decrease dex by 50%; if symptoms persist then decrease 50% prn
Metabolism and nutrition disorders	Hyperglycemia Grade 3 or higher, (>250 - 500 mg/dL; >13.9 - 27.8 mmol/L); hospitalization indicated	Treat with oral hypoglycemic agent or insulin prn; decrease by 50% prn	

* Located at http://ctep.cancer.gov/protocolDevelopment/electronic_applications.ctc.htm

** Use the following to describe actions in the Action column:

- Omit = The current dose(s) for the specified drug(s) during a cycle is skipped. The patient does not make up the omitted dose(s) at a later time
- Hold/Delay = The current dose(s) of all drugs during a cycle is delayed. The patient does make up the delayed dose(s) when the patient meets the protocol criteria to restart drugs.
- Discontinue = The specified drug(s) are totally stopped.

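### For Cycle 1 toxicities that are not DLTs by grade, Sections 7.22 and 8 together let the day of onset or recovery decide whether the event counts as a DLT

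*Combined protocol and SAP*

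**What the plan says.** Section 7.22 defines a DLT as a Cycle 1 event, at least possibly related to study medication, that meets a row of its table. Four rows go by type and grade: febrile neutropenia, Grade 4 neutropenia or thrombocytopenia lasting at least 7 days, Grade 4 infection, and other non-hematologic events at "Grade 4 as per NCI Common Terminology Criteria for Adverse Events v 4.0". Two rows go by what happens to dosing:

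- Delay: "Any toxicity that causes a dose delay of >2 weeks of the next intended dose".
- Reduction: "Any dose reduction within cycle 1".

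The dosing rows share one exemption: "Except dose reductions and delays due to rash associated with lenalidomide". Those patients are replaced.

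Section 8.0 makes the dose-modification tables binding in this window: "Strictly follow the modifications in this table for the first" two cycles. Section 8.2 then splits most lenalidomide actions by day of onset:

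- Days 2-14: omit the drug and, if the event recovers to the stated grade before Day 21, "restart lenalidomide at next lower dose level and continue the cycle through Day 21" (for allergic reactions the recovery limit is Day 15).
- Day 15 or later: "Omit lenalidomide for remainder of cycle", with the one-level reduction taken in the next cycle.

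Section 8.11 gives the same deferred reduction when lenalidomide was left out for the rest of the previous cycle, which covers early-onset events that do not recover in time. Section 8.3 has anakinra omitted until recovery and, for the events that call for a reduction, restarted one level lower, with no cut-off day. The notes under Section 8.4 define omission (skipped, not made up) separately from hold/delay (made up later).

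No section says that a reduction first applied at the start of Cycle 2, for a Cycle 1 toxicity, is a DLT.

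**The concern.** Grade 3 thrombocytopenia, Grade 4 thrombocytopenia lasting under 7 days and Grade 3 non-hematologic events are not DLTs by grade. For these, only the two dosing rows can decide. The reduction row looks at the cycle in which the reduction is made, and Section 8 fixes that by the calendar. Two patients with the same event, grade and duration can then be classified differently although every rule was followed exactly.

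The DLT count drives every 3+3 decision. Determining the MTD or MAD is the phase I primary objective (Sections 2.11 and 16.11), and Sections 7.12 and 16.21 carry that dose into phase II.

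**Working it through.** **1. The plan's own table.** Sections 16.222 and 16.223 escalate after 0 of 3 DLTs, or after 1 of 3 followed by 0 of 3. With true DLT rate p:

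e(p) = (1-p)^3 + 3p(1-p)^2 × (1-p)^3 = (1-p)^3 + 3p(1-p)^5

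For p = 10, 20, 30, 40 and 50% this gives 0.906, 0.709, 0.494, 0.309 and 0.172. All agree with Section 16.227 (0.91, 0.71, 0.49, 0.31, 0.17). The table is correct; the question is which events feed it.

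**2. Lenalidomide.** Take a related toxicity that is not a DLT by grade and for which only lenalidomide is modified. Grade 3 thrombocytopenia is the clean case, because Section 8.3 has no anakinra row for it. A Grade 3 non-hematologic event qualifies if the investigator attributes it to lenalidomide alone, as Section 8.2 allows. Assume the Section 8.11 conditions are met and Cycle 2 starts on time on Day 29. The gap is Day 29 minus the first missed day, where there is no restart in Cycle 1.

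| Onset | Recovery | Duration (days) | Reduction made in | Gap (days) | Reduction row | Delay row, if omission counts as delay |
|---|---|---|---|---|---|---|
| Day 10 | Day 13 | 3 | Cycle 1 | – | DLT | – |
| Day 14 | Day 17 | 3 | Cycle 1 | – | DLT | – |
| Day 15 | Day 18 | 3 | Cycle 2 | 29-15 = 14 | no | no (not >14) |
| Day 15 | Day 28 | 13 | Cycle 2 | 29-15 = 14 | no | no (not >14) |
| Day 14 | Day 22 | 8 | Cycle 2 | 29-14 = 15 | no | DLT |
| Day 10 | Day 22 | 12 | Cycle 2 | 29-10 = 19 | no | DLT |

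Rows 2 and 3 differ only by one day of onset. Row 4 lasts 13 days and is not a DLT on either reading of delay. The last two rows depend on whether omitted doses are a delay.

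**3. Anakinra.** This applies where Section 8.1 lists a lower level, so not at phase I dose level 1. For a Grade 3 non-hematologic event with onset on Day 20, recovery on Day 24 gives a reduced restart in Cycle 1, a DLT. Recovery on Day 30 puts the reduction outside Cycle 1; a restart that day means a gap of 30-20 = 10 days, not a DLT. If Cycle 2 instead waits for the next weekly check under Section 8.11, on Day 36, the gap is 36-20 = 16 days and the delay row might apply. For onset on Day 22 or later, even a Day 36 restart leaves at most 36-22 = 14 days, so the event escapes both rows.

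**4. Replacement rule.** Sections 13.6 and 16.226 replace a patient whose Cycle 1 dose falls below 70% of the expected dose for reasons other than DLT. Omitting lenalidomide from Day 15 leaves 14/21 = 66.7%; from Day 16, 15/21 = 71.4%. If omission counts as a reduction there but not in Section 7.22, the Day 15 patient leaves the DLT denominator and the Day 16 patient stays.

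**5. Illustration of size (assumed rates, not in the documents).** Let 10% of patients have a DLT from the other rows, and independently 20% a toxicity requiring a lenalidomide reduction. Let f be the share of those reductions that fall inside Cycle 1. Then p = 1 - 0.90 × (1 - 0.20f):

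- f = 0: p = 0.10, e = 0.91
- f = 0.5: p = 0.19, e = 0.73
- f = 1: p = 0.28, e = 0.54

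The toxicity burden is the same in all three; only the timing differs.

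**The case against.** The strongest reply is the delay row. On a plain reading, early-onset lenalidomide toxicity not recovered by Day 21 cannot be re-dosed before Day 29, so its gap is at least 29-14 = 15 days and it is a DLT after all. The separate definitions of omission and hold/delay are given for the action columns of Section 8 and are not stated to govern Section 7.22. Section 8.11 also holds Cycle 2 until recovery, which can push a long late-onset event past two weeks. This stands as a partial answer. A reader might infer that longer-lasting toxicities generally escape while brief ones block escalation. The documents do not support that: the delay row may catch many of the longer ones, events that are DLTs by grade are unaffected, and one DLT in three expands the cohort, with two or more needed to stop escalation. The Day 14 versus Day 15 split, the 13-day case and late anakinra events remain.

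One could also argue that omitting doses is itself a reduction in Cycle 1, which would close the gap. Section 8.2, however, names omission and the one-level reduction as separate steps.

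Two other readings go too far. The reduction row does not displace the grade-based rows: the rows are alternatives, and a forced reduction is a legitimate DLT criterion. Nor is it a contradiction that a dexamethasone reduction for persistent low-grade dyspepsia (Section 8.4) could count. On its face the row covers every agent, Section 16.2 studies the combination, and the event must still be attributed to study medication. What is missing is a statement of which agents count.

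Finally, under Addendum 5 phase I patients go off study treatment. The documents do not expressly say that phase I accrual is complete; if it is, new wording would affect only how the MTD/MAD is reported and carried forward.

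**Conclusion.** The point holds in a limited form. Followed exactly, Sections 7.22 and 8 give inconsistent DLT calls for toxicities that are not DLTs by grade: onset before or after Day 15 decides for lenalidomide, and recovery before or after the end of Cycle 1 decides for anakinra. The delay row narrows this for early-onset lenalidomide toxicity if omission counts as delay, which the text leaves open.

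The size in this trial cannot be computed, because the documents give no toxicity rates or timing. The range 0.91 to 0.54 per level rests on the assumed 10% and 20% and on independence. It shows sensitivity to timing. A reader might take it as proof that the reduction row wrongly depresses escalation; it is not, since counting the deferred reductions as well would also be consistent and would lower the probability.

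**What to change.** Reconcile the reduction and delay rows of Section 7.22 with Sections 8.11 and 8.2 to 8.4 and with the replacement rule in Sections 13.6 and 16.226. The text should:

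- classify a Cycle 1 toxicity that requires a reduction the same way whether the reduction is applied within Cycle 1 or at the start of Cycle 2;
- state whether omitted doses count as a delay, or as a reduction, in Section 7.22 and in the replacement rule;
- state which agents' reductions count.

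Which rule to adopt is for the sponsor; no clinical threshold is proposed. The cost is a small wording change to two table rows, their footnote and the matching replacement text. Any phase I patients already treated would need their DLT status rechecked under the clarified rule, and the MTD/MAD reported accordingly.

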7.3 Lenalidomide supply

Patients will receive lenalidomide every 28 days. All unused study drug must be returned to Mayo Clinic to be recorded. Study drug is to be handed back to the patient to return as per Revlimid REMS. **Only enough lenalidomide for one cycle of therapy will be supplied to the patient each cycle.**

7.4 Stem cell collection

Treatment can be interrupted for the purpose of collecting stem cells. Patients can be restarted on protocol therapy after stem cell collection as long as criteria for initiation of a next cycle are met at the time of therapy initiation (Section 8.11).

7.5 Stable plateau

Patients that achieve a stable plateau after 2 years of therapy may be tapered to lower doses of lenalidomide and/or dexamethasone at the discretion of the treating physician

When the patient discontinues all study medication, the MCCC Registration Office must be called [contact]) to find out which study therapy the patient was receiving. Appropriate procedures for gradually reducing the doses of lenalidomide and/or dexamethasone should then be followed.

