7.7 Breaking Codes in Double-Blinded Studies

Situations requiring codes to be broken: There are three distinct situations in which it is appropriate to break the codes for individual patients enrolled in double-blind trials:

- (1) In the event of an emergency for an individual patient.
- (2) In the event that it would be helpful for the future clinical care of an individual patient after she/he has completed participation in the trial.
- (3) When it is necessary to know the specific treatment assignment of each patient in the trial in order to manage them all appropriately after they have completed participation in the trial. Example: There is a blinded arm that contains a steroid, narcotic, or other medication that must be carefully reduced in order to prevent physiological damage. [This one is rare--there are no currently active protocols of this type.]

In the event of an emergency, call the MCCC Registration Office at [REDACTED] to break the code on Monday through Friday, 8:00 a.m. to 4:30 p.m. Central Time. If the code must be broken after hours, assume the patient was assigned to active treatment and treat accordingly. Place a call to the MCCC Registration Office and leave a message informing them of the need to un-blind a patient. Provide your contact information so that MCCC Registration Office personnel can return the call the next business day.

If, in the judgment of the attending physician, it would be helpful for the future clinical care of the individual patient, the code may be broken *after* the patient has completed the study. That is, after the patient has been fully evaluated and all evaluation information has been recorded by the attending physician and the patient (if appropriate), the MCCC Registration Office may be called [REDACTED] to find out which study therapy the patient was receiving.

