NOTE: If the patient experiences a significant adverse event requiring a dose reduction at the start of the next cycle, then the dose will remain lowered for that entire subsequent cycle. If that cycle is

completed with no further adverse events >Grade 2, then the dose may be increased, at the investigator's discretion, one level at a time, in the following cycles.

NOTE: Adverse events requiring a dose-reduction step for any or all drugs beyond the two dose-reduction steps (levels –1 and –2) will be at the discretion of the treating physician, if the decision is made for the patient to be kept on study. These dose reductions must be clearly recorded in reported clinical data.

NOTE: Patients in whom one or more of the study treatment agents have been discontinued will remain on study unless all study treatment agents are discontinued. Patients in whom all study treatment agents were discontinued will proceed to event monitoring (see [Section 18.0](#)).

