13.0 Treatment/Follow-up Decision at Evaluation of Patient

NOTE (Phase I Only): As of Addendum 5, Anakinra will no longer be provided and all patients will go off study treatment. Event monitoring will no longer be required. Patients may obtain Anakinra commercially and be treated off study

- 13.1 Responding to treatment
Patients who are sCR, CR, VGPR, PR, or SD (or usCR, uCR, uVGPR, uPR) will continue treatment per protocol.
- 13.2 Treatment continuation
In the absence of treatment delays due to adverse event(s), treatment may continue until one of the following criteria applies:
 - 13.21 Progression requiring treatment for active myeloma
 - 13.22 Unacceptable toxicity and ineligibility for retreatment.
 - 13.23 Patient refusal of continued treatment.

All attempts should be made to complete the End of Study procedures if a patient withdraws from the trial early. The patient will then go to event monitoring per Section 18.0.

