13.3 Ineligible patients

A patient is deemed ineligible if at the time of registration, the patient did not satisfy each and every eligibility criteria for study entry. The patient may continue treatment off protocol at the discretion of the physician as long as there are no safety concerns, and the patient was properly registered. The patient will go directly to the event-monitoring phase of the study.

- If the patient received treatment, all data up until the point of confirmation of ineligibility must be submitted. Event monitoring will be required per section 18.0 of the protocol.
- If the patient never received treatment, on-study material and the End of Active Treatment/Cancel Notification Form must be submitted. No further data submission is necessary.

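### Section 7.5 can disclose a phase II patient's arm when all study medication stops, while time to progression is still being followed, and it is not reconciled with Section 7.7

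*Combined protocol and SAP*

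**What the plan says.** Section 7.5 (Stable plateau) first allows lenalidomide and/or dexamethasone to be tapered, at the physician's discretion, in patients with a stable plateau after 2 years. It then says: "When the patient discontinues all study medication, the MCCC Registration Office must be called", the purpose being to learn which therapy the patient had. It continues: "Appropriate procedures for gradually reducing the doses of lenalidomide and/or dexamethasone should then be followed". No condition about progression or completed data is attached.

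Section 7.7 lists three situations for breaking the code:

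- an emergency;
- the future care of an individual patient who has completed participation. This is optional, and the section explains its timing: "That is, after the patient has been fully evaluated and all evaluation information has been recorded by the attending physician";
- a need to know every patient's assignment "in order to manage them all appropriately after they have completed participation in the trial". The example is a blinded drug, such as a steroid, that must be reduced carefully, and the section adds: "This one is rare--there are no currently active protocols of this type".

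Other sections bear on what completion means. The notes closing Section 8.4 say that patients who have stopped one or more agents "will remain on study unless all study treatment agents are discontinued", and that those who have stopped all agents go to event monitoring. Section 13.2 lists toxicity and refusal as reasons to stop, besides progression. It adds "All attempts should be made to complete the End of Study procedures if a patient withdraws from the trial early", followed by event monitoring. Section 13.3 treats event monitoring as part of the study: "The patient will go directly to the event-monitoring phase of the study". Section 18.13 collects event monitoring forms every 6 months until progression, with no follow-up required beyond 3 years from registration. Section 16.11 runs TTP from registration to documented progression and censors at the last disease assessment if new treatment comes first.

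**The concern.** The phase II comparison is double-blind and its primary endpoint is TTP. The trigger in Section 7.5 is the end of drug, not the end of endpoint follow-up. For a patient who stops for toxicity, by refusal or on a plateau, the two can be months or years apart.

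Once the arm is known, two decisions can be affected. One is when to start new therapy, which censors TTP and which no protocol threshold governs. The other is the remaining judgement in calling progression: Table 11.5, footnote g, lets treatment stop for unconfirmed progression at the physician's discretion and has it recorded as progression. No blinded review of progression is described. If either decision differed by arm, the log-rank comparison would be affected through informative censoring or through event ascertainment.

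**Working it through.** **1. The plan's own event count.** Section 16.31 gives medians of 20 and 40 months, 45 patients per arm, 1:1 allocation, one-sided alpha 0.05, 80% power and 52 progressions. By Schoenfeld's formula, events = 4(1.645 + 0.842)² / (ln 2)² = 51.5, rounded up to 52. The figure reproduces and is not in dispute.

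Expected events, taking exponential TTP, S(t) = 0.5^(t/median), uniform entry over 24 months and analysis at month 48: follow-up F = 48 − entry month is uniform on 24 to 48. The mean of S(F) is 0.2955 (control) and 0.5398 (experimental). Events are 45 × 0.7045 = 31.7 and 45 × 0.4602 = 20.7, a total of 52.4.

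**2. The two rules side by side.**

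| | Section 7.5 | Section 7.7, non-emergency |
|---|---|---|
| Trigger | all study medication stopped | participation completed |
| Force | mandatory | optional for individual care |
| Data condition | none | for individual care: full evaluation, all evaluation data recorded |
| Progression or event monitoring | not mentioned | not mentioned |
| Who is covered | unclear: plateau patients or everyone | any patient |

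Whether the timing conflicts depends on when participation ends. Sections 8.4 and 13.2 can be read as ending it when all agents stop. Section 13.3 and the explanation in 7.7 point to a later date. On either reading, a patient who stops before progression goes to event monitoring and remains at risk for TTP, so the endpoint is open when 7.5 applies.

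**3. Exposure if 7.5 covers only plateau patients.** The documents give no rate of stopping, so this takes the extreme case in which everyone progression-free 24 months after registration stops then, with the progression hazard unchanged.

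- Progression-free at 24 months: 45 × 0.4353 + 45 × 0.6598 = 19.6 + 29.7 = 49.3 of 90.
- Events up to 24 months: 45 × 0.5647 + 45 × 0.3402 = 25.4 + 15.3 = 40.7.
- Those who stop enter event monitoring, so follow-up ends at min(F, 36). The mean of S(min(F, 36)) is 0.3216 and 0.5658.
- Events after disclosure: 45 × (0.4353 − 0.3216) + 45 × (0.6598 − 0.5658) = 5.1 + 4.2 = 9.3.
- Total: 40.7 + 9.3 = 50.1 before rounding of the parts. Share: 9.3 / 50.1 = 19%.

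If 10% to 50% of these patients stopped, the figure would be 0.9 to 4.7 events. If 50% per year of those who stop then began new therapy, which censors, it would be 0.7 to 3.6.

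**4. Exposure if 7.5 covers anyone who stops.** With assumed annual stopping probability p, let s = −ln(1 − p)/12 and λ = ln 2/median. With G = min(F, 36), a patient's chance of an event after stopping is (1 − e^(−λG)) − [λ/(λ + s)](1 − e^(−(λ + s)G)), averaged over F, multiplied by 45 and summed over arms. Total events add those that occur before stopping, up to F.

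| Assumed stopping per year | Events after disclosure | Total events | Share |
|---|---|---|---|
| 10% | 5.7 | 51.7 | 11% |
| 20% | 10.9 | 51.2 | 21% |
| 30% | 15.8 | 50.8 | 31% |

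If 50% per year then start new therapy, the events after disclosure fall to 3.4, 6.5 and 9.3. All these numbers count events in patients whose arm is known. None measures bias.

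**The case against.** The strongest reply is that 7.5 is a narrow, practical sentence about plateau patients, and that little discretion is left once drug stops. Parts of this stand:

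- The heading may limit the sentence to plateau patients, and Section 13.2 lists no stop for plateau, so the group could be small.
- Progression is itself a reason to stop. For those patients the endpoint is already closed and disclosure does no harm to it.
- M-protein thresholds and two consecutive assessments constrain the calling of progression. Its documentation goes to quality assurance staff (Sections 18.12 and 18.13), and progression based on skeletal disease alone should be discussed with the Study Chair (Section 11.4). None of these steps is said to be blinded, and none governs when new therapy starts.
- Masking may already be imperfect: the placebo is saline, and injection site reactions occur in more than 10% of patients on anakinra. Even so, a guess differs from a disclosed assignment.

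A reader might also infer more than the text supports:

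- **That completion is undefined.** Section 7.7 does explain it, as full evaluation with all evaluation information recorded. The gap is that the explanation is not tied to progression or to the end of event monitoring.
- **That situation (3) of 7.7 authorises the call.** Its example is a blinded drug needing careful reduction. Here lenalidomide and dexamethasone are given in both arms and only anakinra or placebo is blinded. The section also says that no active protocol is of that type.
- **That 11.7 of 52.4 events (22%) is the plateau ceiling.** That figure omits the 3-year limit on follow-up, which would apply to every patient in that scenario.

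**Conclusion.** The point stands in limited form. Sections 7.5 and 7.7 differ in trigger, force and data condition, and following 7.5 as written can disclose the arm of a patient whose primary endpoint is still open. The scope of 7.5 is unclear.

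It would go too far to conclude that the phase II result would be biased, or that most stopping patients would be unblinded early. The documents give no stopping rate, no rate of new therapy and no basis for the direction of any effect. The 9.3 of 50.1 events is an extreme case for plateau patients under exponential TTP at the plan's medians, uniform accrual, analysis at month 48, an unchanged hazard after stopping and no new therapy. The figures for the wider reading rest entirely on assumed rates.

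This is a wording defect that should be corrected. It matters only if phase II proceeds; the note on ending study treatment under Addendum 5 is confined to phase I.

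**What to change.** Amend the text as follows:

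1. In 7.5, make non-emergency disclosure wait until the patient's TTP follow-up is complete, meaning documented progression or the end of event monitoring, and refer to 7.7.
2. In 7.5, state whether the sentence covers plateau patients only or everyone who stops all study medication.
3. In 7.7, say that completed participation and completion of the study have that same meaning, and align the closing notes of 8.4 and the end-of-study wording in 13.2.
4. Leave the emergency provision in 7.7 unchanged.

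The sentence in 7.5 on gradual reduction of lenalidomide and/or dexamethasone now follows the disclosure call. The sponsor should reconcile it with the new timing; no taper or other clinical rule is proposed here.

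The cost is a few sentences in an amendment, with no added patients or visits. The downside is that patients who stop before progression, and their physicians, would wait for routine disclosure until progression or the end of the 3-year follow-up.
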